10.4 Analysis of the main variables of the study

The Cox regression analysis will be performed with the experimental biomarkers and the following prognostic variables (LDH, functional status, age, limited resectable disease (<3 nodules and <5cm). A classification will be performed using the most discriminatory variables. The classification It will be carried out with all the clinical variables of impact in the univariate analysis, including the 4 clinical variables (LDH, functional status, age, limited resectable disease (<3 nodules and <5 cm) and the 3 pathways previously described (BRAF, DP and PTEN). -PI3K) The classification will be carried out with the variables with the greatest impact in the multivariate analysis.

The proposed sample size ensures the construction of a consistent multivariate analysis.

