	
quartiles were calculated according to Brookmeyer and Crowley methods (55,56). Safety data were analysed throughout the entire study.
 
In the first step to develop a prediction model for PFS, univariate Cox regression analysis including all clinical variables collected in the study was performed in order to identify which should be considered for the model selection thereafter in the second step. All factors with a ≤ 0.15 p value (Appendix 15.2, item 4) were selected for the multivariable Cox analysis. The cut-off of ≤ 0.15 p-value was used in order to include the presence of resectable liver metastases as that is a well-known prognostic factor in mCRC. In the second step multivariable Cox regression analysis was performed including those variables identified in the univariate analysis. Importantly, the variable treatment (FOLFIRI vs FOLFOX) was not included for the development of the prediction score because it was not a characteristic intrinsic to the patients.

--	--

12-MONTHS PFS RISK MODEL DEFINITION

Clinical variables and biomarkers were used to build a score to predict 12-months PFS, by using a multivariable Cox regression model built with those clinical variables with a $p \leq 0.15$ in the multivariable analysis (performance status, chemotherapy regimen, sidedness, resectable only liver metastases). Once the first risk score was built adding up the coefficients of the multivariable model ($PS > 0 = 0.6$, left sided = -0.5, resectable liver only metastases = -0.4 and folfiri+cetuximab therapy = Not evaluable), ROC curves were computed for PFS at 12 months using a logistic regression model. All 4 scores (A. Clinical variables including PS, sidedness and resectable only liver metastases, B. Clinical variables + BRAF mutation; C. Clinical variables + PI3K mutation or PTEN ≤ 3 ; D. Clinical variables + DP) had comparable low areas under the curve, ranging between 0.5 and 0.7, overall: The AUC of the score containing the clinical variables was 0.67 (95% CI) (0.60-0.75).

The AUC of the score with clinical variables and BRAF mutational status was 0.68 (0.61-0.75, p-value = 0.37). The AUC of the score with clinical variables and PI3KCA mutation/PTEN status was 0.69 (0.61-0.76, p-value = 0.32). The AUC of the score with clinical variables and DP phenotype was 0.66 (0.58-0.73, p-value = 0.09).

SAFETY RESULTS

CONCLUSIONS

DATE OF THE REPORT:

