6.5.1.5. Analysis of main study variables

The primary efficacy analysis of this trial was performed based on all subjects who provided their informed consents, were included in the trial, and did not present significant protocol deviations throughout the study period. .

Continuous and ordinal variables between independent groups were compared using the Wilcoxon rank-sum test and proportions were compared with Fisher's exact test. Clinical endpoints were ORR, DoR, PFS, and OS. Tumour assessments by CT scans were performed every 3 months until PD. Patients without a second CT scan evaluation were not assessable for ORR.

PFS was defined as the time of the signature of the ICF date until PD or death from any cause. Patients who did not experience PD or death were censored on the date of last examination. For more information regarding censoring see in Section 7.5.1.1. OS was defined as the time from the signature of the ICF date to death from any cause. Patients lost to follow-up or still in the study at database closure have been censored at the date last known to be alive.

Survival analyses including PFS and OS were performed using Kaplan–Meier methods. Cox proportional hazards regression with the Efron method for ties was used to identify prognostic factors for PFS and OS.

Multivariable analysis was performed using subject-matter knowledge and deciding a *priori* the variables to adjust by age (>65 years), sex, tumour site (right vs left), surgery of primary tumour, liver only metastases (<3 nodules and <5 cm vs >3 nodules or >5 cm), ECOG PS, LDH (>450 U/L) and CEA, BRAF mutational status, and type of therapy. This analysis was later adjusted by variables with p-values <0.10 in the

univariate analysis via the automated stepwise selection of variables (p-value for variable entry into the model was 0.2 and p-value to keep the variable in the model was 0.1).. All p-values were two sided.

The proposed sample size ensures establishing a consistent multivariable analysis. Clinical variables and biomarkers were used to build scores intended to predict 12- months PFS as following:

1. A multivariable Cox model was built with those clinical variables that in the univariate analysis had a p-value ≤ 0.15 (PS, chemo regimen, sidedness, resectable liver metastases).

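### The clinical score that serves as comparator for the primary AUC analysis is defined by inconsistent, data-driven selection rules, and the Cox adjustment set is left open between a fixed list and stepwise selection

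*SAP*

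**What the plan says.** SAP 6.5.1.1 defines the primary comparison: the AUC of a clinical score against the AUC of that score plus each biomarker. The clinical part is described in several places.

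- **Protocol 10.4** starts from the clinical variables of impact in the univariate analysis, "including the 4 clinical variables (LDH, functional status, age, limited resectable disease"). It then says: "The classification will be carried out with the variables with the greatest impact in the multivariate analysis". No p-value threshold is given.
- **SAP 1, Statistical methods** screens all clinical variables by univariate Cox regression at p≤0.15, then fits a multivariable model. It says the cut-off "was used in order to include the presence of resectable liver metastases", a known prognostic factor. It also says regimen was left out of the score because it is not intrinsic to the patient.
- **SAP 1, risk model definition** builds the score from variables with p≤0.15 "in the multivariable analysis (performance status, chemotherapy regimen, sidedness, resectable only liver metastases"). It gives coefficients of 0.6 (PS>0), -0.5 (left-sided) and -0.4 (resectable liver-only), and enters FOLFIRI as not evaluable. It lists Score A as PS, sidedness and resectable liver metastases.
- **SAP 6.5.1.5, score steps**: "A multivariable Cox model was built with those clinical variables that in the univariate analysis had a p-value" of at most 0.15, naming PS, regimen, sidedness and resectable liver metastases. Score 1 is then described with all four, regimen included.
- **SAP 6.5.1.5, multivariable analysis**: an adjustment list decided a priori (including age, sex, tumour site, LDH, CEA, BRAF and therapy), followed by "This analysis was later adjusted by variables with p-values <0.10" in the univariate analysis, with automated stepwise selection (entry 0.2, stay 0.1).

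**The concern.** A marker's added value is measured against a comparator, so the comparator should be fixed before the data can influence it. Here the filter is univariate in one place and multivariable in another, and the cut-off was set to let a named variable through. A variable that is known to matter can simply be forced in, as Protocol 10.4 already allows. SAP 4.2 also describes LDH (with performance status) as prognostic in all previous randomised trials, yet LDH is not in the score and no reason is given. Whether regimen is in Score 1 depends on which section is read.

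The second issue concerns the hazard ratios. The output shells call for an adjusted hazard ratio (OS by BRAF) without saying whether it comes from the a-priori list or from the stepwise model. If from the stepwise model, its confidence interval takes no account of the selection.

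**Working it through.** **1. The passages side by side**

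- Filter: univariate p≤0.15 (SAP 6.5.1.5 and SAP 1, Statistical methods) against multivariable p≤0.15 (SAP 1, risk model definition).
- Regimen: excluded (SAP 1, Statistical methods; absent from Score A) against included (SAP 6.5.1.5, Score 1).
- LDH and age: candidates in Protocol 10.4, absent from every SAP score, no reason stated.
- Sidedness: in every SAP score, not named in Protocol 10.4.

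**2. The plan's own figure**

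The SAP reports a clinical AUC of 0.67 (0.60-0.75) with 181 patients analysed for efficacy. The planning rates of 50% and 30% with a 40/60 split give an overall 12-month PFS of 0.4×0.50+0.6×0.30 = 0.38 or 0.6×0.50+0.4×0.30 = 0.42. I use 0.40, so about 109 patients with an event by 12 months and 72 without, assuming all 181 can be classified.

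Hanley-McNeil: A/(2-A) = 0.67/1.33 = 0.504 and 2A²/(1+A) = 0.898/1.67 = 0.538. The standard error is 0.040, so the interval is 0.67±1.96×0.040 = 0.59 to 0.75, consistent with the SAP.

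**3. How far one variable moves the clinical AUC**

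The documents give no prevalences for the score variables, so these are assumptions. The model is S(12|x) = exp(-m·exp(0.6·PS - 0.5·left - 0.4·resectable)), with m solved so that mean 12-month PFS is 0.40. AUC = P(score higher in an event patient) + ½·P(tie), computed exactly over the eight score patterns. With PS>0 in 50% and left-sided tumours in 70%, the AUC with and without the resectable variable is (differences taken before rounding):

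- prevalence 5%: 0.653 and 0.648, change -0.005
- 10%: 0.657 and 0.647, change -0.009
- 15%: 0.660 and 0.647, change -0.013
- 20%: 0.664 and 0.647, change -0.017
- 25%: 0.666 and 0.646, change -0.020

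Over a wider grid (PS>0 40-60%, left 65-80%, PFS 38-50%) the change is -0.004 to -0.023. In 4,000 simulated data sets of 181 patients (resectable 15%, PFS 42%) it averages -0.013 with SD 0.012. It is at least 0.01 in size in 63% of data sets and at least 0.02 in 28%.

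The reported marker changes are 0.68-0.67 = +0.01 (BRAF), 0.69-0.67 = +0.02 (PI3K-PTEN) and 0.66-0.67 = -0.01 (DP).

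**4. Other changes of set, on the same model**

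- Drop sidedness: -0.022 to -0.042.
- Add regimen with an assumed coefficient of 0.2-0.5: +0.006 to +0.036.
- Replace sidedness by LDH and age, with assumed coefficients 0-0.5 and 0-0.2: -0.041 to +0.022.

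**5. Effect on a marker's gain**

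The primary quantity is the difference between two AUCs, so I added an independent marker to the model, with the resectable variable at 15%. At BRAF's prevalence (20/181 = 11%) and an assumed coefficient of 0.5, the gain is 0.012 with the resectable variable and 0.013 without it. At a coefficient of 1.0 the gains are 0.0375 and 0.0396. At the PI3K-PTEN prevalence (98/167 = 59%) and coefficients of 0.2-0.4, the gain changes by about 0.003. Overall this is about 0.001-0.003, and 0.000-0.005 if the resectable prevalence runs from 5% to 25%.

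**The case against.** A reader might infer that four incompatible rules compete to define the score. The documents do not support that. Protocol 10.4 treats its four variables as required candidates and then keeps those of greatest impact, so it does not fix a final set and is itself data-driven. Both p≤0.15 wordings name the same four variables, so no different set is shown to follow from that mismatch. The stepwise rule belongs to the adjusted Cox analysis: its a-priori list contains BRAF, so it cannot define a clinical-only score.

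A reader might also infer that the cut-off alone is worth as much as any marker, or that the marker results would change. This is not shown either. The SAP gives one clinical AUC, no prevalences and no univariate p-values. That resectable metastases would drop out at a stricter cut-off is inferred from the stated reason for choosing 0.15. Changing the clinical set moves all four scores together, so most of the shift cancels in the comparison. The reported marker comparisons (p = 0.37, 0.32 and 0.09) are all above 5%, and nothing here suggests otherwise.

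Finally, using only the protocol's four variables would discard sidedness, whose coefficient is larger in size than that of resectable metastases. A weaker comparator could flatter the markers. That objection stands, and the fix allows for it.

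**Conclusion.** The concern holds as an inconsistency in the definition of the primary comparator. The contradiction over regimen is the firmest part and needs no assumption. The univariate/multivariable mismatch, the cut-off set to admit one variable and the unexplained absence of LDH and age can all be read directly from the text. The fixed-list-or-stepwise ambiguity for the hazard ratios is a separate, equally plain gap.

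The numerical consequence is modest and conditional. Dropping the resectable variable moves the clinical AUC by about 0.005-0.02. This rests on the SAP's coefficients, proportional hazards, 12-month PFS near 40% and an assumed prevalence of 5-25%. The shift matches the reported marker changes in order of magnitude, but the effect on a marker's gain is several times smaller.

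**What to change.** - Define Score 1 as one fixed clinical set with no p-value filter: LDH, performance status, age and limited resectable disease, with the coding of each written down. Add each marker to that model.
- Report the same comparison with sidedness added, alongside, so that the benchmark is not weakened.
- Reconcile SAP 1 and SAP 6.5.1.5 on whether regimen is in the score, and say why LDH and age were left out of the selected one.
- Keep the a-priori list in SAP 6.5.1.5 as the only adjustment set for hazard ratios, and say so in the output shells.
- Label the p≤0.15-selected score and the stepwise results exploratory.

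The cost is SAP wording and a re-run on data already collected. One or two weak covariates stay in the model, and one extra AUC comparison is reported.

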10.2.5 Considerations about the sample size

Two groups will be defined based on the classification constructed from the clinical variables and the proposed biomarkers.

The Log-rank method has been used instead of a binomial method for the sample calculation in order to include all the events that occur during follow-up.

A minimum difference of 20% (60 vs. 40%) in PFS is expected at 12 months between groups and with the following assumptions:

Alpha error (bilateral): 5%

Beta error: 20%

Monthly recruitment: 8 patients

Percentage of patients with classification = 0 is 40%

The number of patients required is 155 patients to be recruited in 24 months and a total duration of the trial (recruitment + follow-up) of 28 months for 115 events to occur.

Assuming 10% non-evaluable pts we should include a total of 170 pts.

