2. A score was established for each patient by adding up the regression coefficients of the multivariable Cox model present in these patients. If for example PS>0 was a negative predictor for PFS (i.e. regression coefficient is negative; e.g. -0.5) and left side tumour was a positive prognostic factor (regression coefficient was positive, e.g. 0.6) then for a patient with PS>0 and left sided tumour the two scores were added (-0.5 + 0.6=0.1). If a patients has PS=0 then the score to be added is 0, as it is the case for right sided tumour in the example.
3. Using a logistic regression model for the outcome 12-months PFS, a ROC curve was computed to choose the score cut point that classifies most patients correctly 4. Patients were dichotomized according to that cut point.
5. Steps 2 to 4 were repeated, adding each of the three biomarkers.
6. Definition of the discriminating power of the 4 scores for prognosis of or 12-months PFS according to these results were compared via ROC curves.
7. Determination of the most suitable score for 12-months PFS according to these results.

The four scores included in the first multivariate model using clinical factors where PS>0, chemotherapy with FOLFIRI and cetuximab, left sided and resectable liver metastases were considered (Score 1). The additional scores considered the four clinical factors above plus the status of each biomarkers (Score 2: BRAF mutation; Score 3: PI3K mutant or PTEN ≤ 3) and Score 4: Double-positive Phenotype (DP).

All analyses were performed using SAS V9.3 (SAS Institute, Cary, NC, USA) statistical software.

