6.5.2. DETERMINATION OF SAMPLE SIZE

It was the aim of the study to identify two groups based on the well-established categories of clinical variables and the proposed biomarkers which are prognostic regarding PFS. The sample size should be sufficient detect a clinically relevant difference in PFS with a log-rank test between the two groups, given the following assumptions:

- The difference in PFS at 12 months between the two groups is at least 20% (i.e. 50% vs 30%) corresponding to a hazard ration of 1.79 assuming an exponential distribution. • Alpha error (two-tailed): 5%
- Beta error: 20%
- Monthly recruitment: 8 patients
- Percentage of patients with classification= 0: 40%

Initially, the number of patients required to be recruited in 24 months was 155 for 115 events to occur. Assuming a 10% proportion of potentially non-assessable patients, a total of 170 patients were needed to be included. After recruiting 157 patients, it was determined that about 70 of these patients had insufficient samples for biomarker analysis preventing their inclusion into the analysis of the primary objective. Therefore, in order to observe the 115 events necessary to evaluate the primary endpoint, the total number of patients was increased up to 221 recruited in 47 months (4–5 patients per month). Finally, the total study duration was 70 months (recruitment + follow-up).

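### The SAP calls the four prediction scores comparable without an interval, margin or power for the AUC difference; its non-significant p-values do not show that BRAF or PI3K-PTEN add nothing

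*SAP*

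**What the plan says.** SAP 6.5.1.1 (Primary endpoint) compares the AUC of a clinical score with the AUC of the same score plus each biomarker, for 12-month PFS. Steps 6 and 7 of SAP 6.5.1.5 have the four scores compared by ROC curves and end with "Determination of the most suitable score for 12-months PFS according to these results". Neither section names a test, an alpha for this comparison, a minimum AUC gain, an equivalence margin or a power.

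The SAP Synopsis, under the 12-month PFS risk model, already gives the answer: the scores "had comparable low areas under the curve, ranging between 0.5 and 0.7". The clinical score has an AUC of 0.67 (0.60-0.75). For the first biomarker the text reads "The AUC of the score with clinical variables and BRAF mutational status was 0.68 (0.61-0.75, p-value = 0.37". PI3K-PTEN follows with 0.69 (0.61-0.76, p = 0.32) and DP with 0.66 (0.58-0.73, p = 0.09). Every interval is for a single AUC. The Conclusions entry is blank.

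The only power statement, in SAP 6.5.2, is for a log-rank test between two groups formed from clinical variables and biomarkers together. The difference in 12-month PFS "is at least 20% (i.e. 50% vs 30%) corresponding to a hazard ration of 1.79 assuming an exponential distribution". Protocol 10.2.5 has instead: "A minimum difference of 20% (60 vs. 40%) in PFS is expected at 12 months between groups".

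**The concern.** A statement that four scores are comparable is a claim of similarity. It needs either a margin or an interval for the difference that is narrow enough to be informative. Intervals for single AUCs do not serve, because the scores are computed on largely the same patients and share their clinical terms, so their errors are strongly correlated. A p-value above 0.05 serves only if the test would probably have detected a gain worth having.

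The rare markers make this doubtful: SAP Table 6 has 20 BRAF-mutant and 23 DP patients among 181. A binary marker that few patients carry can have a substantial hazard ratio and still barely move an AUC. What is at stake is the answer to the primary objective. A result that leaves the matter open could be read as showing that the biomarkers contribute nothing.

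**Working it through.** **1. The plan's own figures.** Exponential conversion of 50% versus 30% gives ln(0.30)/ln(0.50) = 1.737. For 60% versus 40% it gives ln(0.40)/ln(0.60) = 1.794. The 1.79 printed in SAP 6.5.2 therefore belongs to the protocol's rates, not to the SAP's.

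The 115 events reproduce with the Freedman formula, two-sided 5%, 80% power, 40/60 split (k = 1.5) and HR 1.79:

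E = (1.960 + 0.842)² × (1 + 1.5 × 1.79)² / [1.5 × (0.79)²] = 7.849 × 13.58 / 0.936 ≈ 114.

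With HR 1.737 the same formula gives 126. This calculation says nothing about an AUC comparison.

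**2. Simulation of the AUC comparison (steps 1 to 6 of 6.5.1.5).**

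Inputs from the SAP:
- clinical coefficients 0.6 (PS > 0), -0.5 (left-sided), -0.4 (resectable liver-only), from the Synopsis;
- marker prevalences 20/181 = 11.0% (BRAF), 23/181 = 12.7% (DP) and 98/167 = 58.7% (PI3K-PTEN), from Table 6.

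Assumed, because the documents do not give them:
- prevalences of PS > 0, left-sided and resectable liver-only of 40/75/10%, 50/70/20% or 60/60/30%;
- overall 12-month PFS of 38% or 50% (38% is 0.4 × 50% + 0.6 × 30%);
- exponential PFS, no censoring before month 12, marker independent of the clinical factors;
- a paired DeLong test at two-sided 0.05;
- a marker HR of 1.737 or 1.794.

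Cox scores were refitted with and without the marker, 800 trials per cell. The simulated clinical AUC was 0.64-0.68, in line with the SAP's 0.67.

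| Marker | Missed at HR 1.737 | Missed at HR 1.794 | Mean AUC gain (HR 1.737) |
|---|---|---|---|
| BRAF | 84-91% | 82-91% | 0.015-0.018 |
| DP | 83-90% | 82-90% | 0.017-0.021 |
| PI3K-PTEN | 71-81% | 70-80% | 0.033-0.044 |

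With coefficients fixed at their true values, the rates at HR 1.737 / 1.794 are 84% / 80% (BRAF), 82% / 79% (DP) and 75% / 69% (PI3K-PTEN). With no marker effect the test rejects in only about 2-3% of trials (BRAF and PI3K-PTEN scenarios), so it is conservative.

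**3. The same data by another route.** The Wald test of the marker coefficient in the Cox model has about 63-73% power for BRAF and DP and 90-93% for PI3K-PTEN. The adjusted hazard ratio carries much more information than the AUC p-value.

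**4. What the printed results imply, roughly.** If each p-value is a two-sided normal test of the difference between the printed AUCs, then SE = |difference|/z, with z = 0.90, 0.99 and 1.70 for p = 0.37, 0.32 and 0.09.

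- BRAF: 0.01/0.90 = 0.011, so 0.01 ± 0.022, or about -0.01 to 0.03. A gain of 0.02 lies inside.
- PI3K-PTEN: 0.02/0.99 = 0.020, so 0.02 ± 0.039, or about -0.02 to 0.06. A gain of 0.04 lies inside.
- DP: 0.01/1.70 = 0.006, so -0.01 ± 0.012, or about -0.02 to 0.00. A gain of 0.02 lies outside; a loss of up to about 0.02 does not.

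These are indications only. The AUCs are rounded to two decimals, the test is unnamed, and PI3K-PTEN status covers 167 patients rather than 181.

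**The case against.** The strongest reply is that the Synopsis sentence is descriptive. It lists four close point estimates and calls them comparable. No sentence derives this from p > 0.05, steps 6 and 7 contain no significance rule, and the Conclusions entry is blank. That stands. A reader might infer that the SAP concludes comparability because the tests were non-significant, or that BRAF and DP will be discarded; the documents say neither. What remains is that this sentence is the only answer given to the primary question, and nothing beside it can support similarity.

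Second, AUC gains of 0.02 are small in discrimination, so the scores might fairly be called close. This is arguable, but it needs a stated margin, and none exists. Association with PFS and improvement in prediction are also different estimands, so a hazard ratio should accompany the AUC difference, not decide it.

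Third, the target effect is defined for combined groups with a 40/60 split, not for one marker added to a clinical score. This is correct, and the single-marker HR is an assumption here.

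Fourth, it is tempting to say that even a BRAF hazard ratio estimated at 1.0 could not exclude 1.79. On 115 events the 95% CI factor is exp(1.96/√(115 × 0.1105 × 0.8895)) = 1.791, but at 116 events it is 1.787, and for DP at 115 it is already 1.73. The actual event count is probably higher. Recruitment of 47 months within 70 leaves at least 23 months of potential follow-up. With 38% PFS at 12 months, exponential PFS and no dropout, 181 × (1 - 0.38^(23/12)) ≈ 152 events, and the BRAF factor is then 1.66. That stronger claim is not supported, and no marker hazard ratio for PFS is printed.

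Finally, part of the remedy is already planned. The Synopsis mentions multivariable analyses of BRAF and PI3K-PTEN, 6.5.1.5 includes BRAF in an adjusted model, and the Section 7 template has an adjusted hazard ratio for BRAF and OS. None of these covers all three markers for PFS.

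**Conclusion.** The point holds as a matter of reporting and decision rule on the primary objective. At a single-marker HR of 1.74 to 1.79, a paired AUC test would miss the effect in roughly 70-91% of trials. That range is not fixed by the documents; it rests on the assumed clinical-factor prevalences, 12-month PFS, absence of early censoring and the DeLong test. Within it, BRAF and DP lie at about 80-90% and PI3K-PTEN at about 70-80%.

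The p-values of 0.37 and 0.32 therefore do not show that BRAF or PI3K-PTEN add nothing. DP is different: its point AUC fell from 0.67 to 0.66, so it should not be read as a missed gain, but without a margin and an interval equivalence is not shown for it either. The discrepancy between 1.79 and 1.737 moves the miss rates by only a few points.

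**What to change.** In SAP 6.5.1.5 step 6 and in the Synopsis, report for each of the three markers:

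- the paired AUC difference from the clinical score, on the patients with that marker measured, with its 95% CI and the test named;
- the PFS hazard ratio adjusted for the clinical score variables, with its 95% CI, based on the actual event count.

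Replace *comparable* in the Synopsis with *improvement in discrimination not shown*, and state from the intervals which effect sizes are excluded and which are not. Do not use 1.79 as a pass/fail limit. It comes from a different comparison, and it must first be reconciled with 50% versus 30%, which gives 1.737.

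The cost is two intervals per marker, largely from models already planned, and some rewording. No new data are needed. The downside is slightly more reporting and a less definite negative conclusion.
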